#### 16.5 Secondary and Tertiary Outcomes and Safety Analyses

Separate analysis plans will be prepared for the renal outcomes and health economic outcomes. A separate plan will also be prepared to examine alternative ways to analyse adherence to the transfusion strategies, as well as any future exploratory analyses. For the secondary outcomes, the treatment effect and two-sided 95% CI for each outcome will be estimated by unadjusted analyses using the same variables as for the primary outcome unless otherwise stated, as appropriate. Both PP and ITT analyses of the secondary outcomes will be performed.

For dichotomous outcomes, risk differences and odds ratios along with 95% confidence intervals will be reported for the unadjusted analyses while the odds ratio will be used for adjusted analyses employing logistic regression. For continuous outcomes, mean differences and adjusted mean differences (from linear regression models) will be reported along with 95% confidence intervals. Other outcomes such as length of hospital and ICU stay, and duration of mechanical ventilation may be inappropriate for standard linear regression models, in which case a transformation (e.g. logarithm) or alternate model (e.g. time-to-event) will be considered. Adjusted analyses will be performed using the appropriate regression framework. Time to death at 6 months will be summarised by Kaplan-Meier curves.

Adherence will be summarised by group; we will also describe the distribution of the location of the non-adherent events (operating room, ICU, ward). The mean haemoglobin value (a) prior to non-adherent RBC transfusion events and (b) for non-adherent trigger events will be reported, by group.

#### 16.6 Interim Analyses

One interim analysis will be undertaken after 50% of patients have reached determination of the primary outcome. A group sequential design has been employed that applies a one-sided boundary. The boundary is based on a Hwang-Shih-DeCani spending function for efficacy. If the boundary is crossed, there will be a non-binding recommendation to stop the trial for benefit. We will only conduct additional safety reviews if otherwise directed by the Data and Safety Monitoring Board (DSMB). The following table shows the Z-statistics for the non-binding recommendation to stop the trial due to benefit.

Analysis	Z-statistic
Interim	2.75
Final	1.98

#### 16.7 Planned Subgroup Analyses

We will conduct subgroup analyses of the primary outcome to determine if the effect of the transfusion strategy varies according to the subgroups below. These analyses will be exploratory only. Subgroup analyses will be accompanied by a test for a treatment by subgroup interaction. Additionally, subgroup specific treatment effects and treatment by subgroup interactions will be estimated with an adjusted model using all of the covariates listed below and a single term for interaction between treatment and sub group defined by each covariate of interest. This procedure will be repeated for each covariate to model adjusted subgroup specific estimates. Tests for trend across ordered subgroups of left ventricular function will be derived in an analogous manner. P values, effect estimates and 95% confidence intervals will be reported as estimated from crude and adjusted models.

Subgroup analyses will be performed based on the following criteria:

1. Age

Page **36** of **55** 

IRAS ID: 325425

- 2. Sex
- 3. Diabetes (with and without insulin)
- 4. Baseline creatinine >200 (as collected for baseline EuroSCORE I)
- 5. Baseline preoperative haemoglobin
- 6. Pre-existing pulmonary disease (as collected for baseline EuroSCORE I)
- 7. Type of surgery: Coronary artery bypass graft (CABG) only, CABG with another procedure, other procedure only (non-CABG)
- 8. Left ventricular function (Good, Moderate, Poor, Very Poor)

#### 16.8 Sensitivity Analysis

We will fit a random-effects model that accounts for the variation between sites in the between group difference of the primary composite outcome. We will also conduct an analysis of the primary composite outcome adjusted for variables that have a clinically significant difference between groups at baseline. In additional sensitivity analyses, we will determine whether analyses of specific patient subsets, as defined below, yield similar results for the primary outcome:

- 1. Excluding patients with any non-adherence to the assigned transfusion strategy
- 2. Excluding patients whose haemoglobin was never measured below 95g/L from the time of randomisation to the end of the index hospitalisation period
- 3. Excluding patients who did not receive any RBC transfusions from the time of randomisation to the end of the index hospitalisation period
- 4. Excluding patients who had at least one protocol suspension from the time of randomisation to the end of the index hospitalisation period
- 5. Excluding patients randomised according to physiologic triggers
- 6. Including only patients of the PP population

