## 7. Introduction, background and scientific rationale

#### 7.1 Background and rationale

Cardiac surgery is one of the most frequent surgical procedures, with approximately 35,000-40,000 procedures conducted in Canada each year. Fifty percent of patients undergoing cardiac surgery are <65 years. Anaemia in these patients is common due to underlying conditions and haemodilution during cardiopulmonary bypass (CPB). Perioperative anaemia has been associated with a significant increase in cardiac (myocardial infarction) and non-cardiac (renal failure and stroke) adverse events and mortality. Patients undergoing cardiac surgery receive a high proportion of RBCs to decrease the risks associated with anaemia (approximately 14% to 20% of the blood supply is consumed by cardiac surgical patients); although there are potential benefits to transfusion, transfusion is costly, often in short supply and may also lead to considerable mortality and morbidity. Restrictive transfusion triggers have been suggested to be preferred by RCTs in many patient populations including critically ill patients, patients undergoing hip fracture surgery, and with acute upper gastrointestinal bleeding.

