#### 11. Trial intervention

#### 11.1 Description of the Trial Intervention/Transfusion Strategies

Trial participants will be randomised to one of the following transfusion strategies in a 1:1 manner:

• **Group 1: Restrictive transfusion strategy:** patients will receive a RBC transfusion if their Hb concentration is <75 g/L (<7.5 g/dL; <4.7 mmol/L) intraoperatively and/or postoperatively.

Page **24** of **55** 

IRAS ID: 325425

• **Group 2: Liberal transfusion strategy:** patients will receive a RBC transfusion if their Hb concentration is <95 g/L (<9.5 g/dL; <5.9 mmol/L) intraoperatively, or postoperatively in the ICU; or <85 g/L (<8.5 g/dL; <5.3 mmol/L) on the ward.

The trial period for intervention will commence on induction of anaesthesia for the index cardiac surgery. When the appropriate Hb trigger is reached, patients in each group will have one unit of RBCs administered followed by repeat determination of the Hb concentration. Each group will be transfused only if their Hb concentration falls below the transfusion threshold. The Hb should be checked before each unit of blood.

The RBC transfusion must take place within the following time frame after the time that the trigger Hb was measured: 2 hours (for patients in the operating room (OR)), 18 hours (in the ICU/Cardiac Care Unit (CCU) or other intensive care environment, including step-down units), or 40 hours (on the hospital ward).

If the investigator decides to perform another intervention, for example re-measuring the Hb or haemoconcentration, and a second Hb value is measured above the trigger within the protocol defined time period (2, 18 or 40 hours, as above), then a transfusion is not required and this would still be considered an adherent "trigger event" (see section 11.5).

Although it is desirable to adhere to the standard triggers, the assigned Hb trigger can be increased to 80 g/L (8.0 g/dL; 5.0 mmol/L) in the restrictive transfusion group or 100 g/L [(10.0 g/dL; 6.2 mmol/L) intraoperative/ICU] / 90 g/L [(9.0 g/dL; 5.6 mmol/L) on the ward] in the liberal transfusion group during an episode of any of the following severe physiologic derangements:

- Mixed/central venous or cerebral oxygen saturation <50%
- Lactate > 4 mmol/L in the absence of the use of epinephrine
- Definitive clinical evidence of active myocardial ischemia as defined by the 4th Universal Definition

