#### 15.2 Secondary Endpoints

The secondary endpoints are as follows; see section 8.12 for definitions and details:

- 1. Incidence of each individual component of the primary outcome: all-cause mortality, myocardial infarction, new onset renal failure requiring dialysis, and new focal neurological deficit (stroke) within 6 months
- 2. Composite and individual all-cause mortality, myocardial infarction, new onset renal failure requiring dialysis, and new focal neurological deficit (stroke) with index hospitalisation or after 28 days postoperatively, whichever comes first Length of stay in the Intensive Care Unit (ICU) and hospital (index hospitalisation)
- 3. Prolonged low output state defined as the need for two or more inotropes for 24 hours or more, intra-aortic balloon pump or ventricular assist device postoperatively (index hospitalisation)
- 4. Duration of mechanical ventilation (index hospitalisation)
- 5. Infection: defined as septic shock with positive blood cultures; pneumonia defined as autopsy diagnosis or roentgenographic infiltrate and at least two out of three of the following criteria: fever, leukocytosis, and positive sputum culture; and/or deep sternal or leg wound infection requiring intravenous antibiotics and/or surgical debridement (index hospitalisation)
- 6. Acute kidney injury (AKI), defined by the Kidney Disease Improving Global Outcomes (KDIGO) clinical practice guideline46 a 50% increase in serum creatinine within 1 week or a 26.5 μmol/L increase within 48 hours (index hospitalisation)
- 7. Delirium, based on one of the following criteria: Confusion Assessment Method (CAM) or CAM-ICU (even on 1 occasion), or Intensive Care Delirium Screening Checklist (ICDSC) > 3, or 3D-CAM, or 4AT ≥4, or more than one dose of haloperidol or similar antipsychotic drug, or documented delirium by neurologist or neurosurgeon or psychiatrist consultation (index hospitalisation)
- 8. Gut infarction confirmed by imaging (e.g. angiography), autopsy, or through surgical means (index hospitalisation)
- 9. Hospital visits (hospitalisation and/or emergency visits and coronary revascularisation at 6 months)
- 10. The proportion of patients transfused and the number of blood products utilised (RBCs, plasma, platelets) (index hospitalisation)

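### Sensitivity analysis item 3 keeps only transfused patients, a group largely determined by the allocated threshold, so it is biased in expectation (probably towards liberal) and cannot test robustness

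*Protocol*

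**What the plan says.** Section 16.8 lists patient subsets in which the primary outcome is re-analysed, to see whether they "yield similar results for the primary outcome". Item 3 is "Excluding patients who did not receive any RBC transfusions from the time of randomisation to the end of the index hospitalisation period". Item 2 is "Excluding patients whose haemoglobin was never measured below 95g/L from the time of randomisation to the end of the index hospitalisation period". The section gives no estimand, adjustment or caution for item 3, whereas section 16.7 calls the subgroup analyses exploratory.

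Section 11.1 defines the arms by the haemoglobin at which red cells are given. In the restrictive arm, "patients will receive a RBC transfusion if their Hb concentration is <75 g/L". In the liberal arm, "patients will receive a RBC transfusion if their Hb concentration is <95 g/L" in the operating room or ICU, with a trigger of 85 g/L on the ward. Section 15.2 lists the proportion of patients transfused as a secondary endpoint, so the protocol itself treats receipt of red cells as a result of the strategy. Section 7.1 states: "Perioperative anaemia has been associated with a significant increase in cardiac (myocardial infarction) and non-cardiac (renal failure and stroke) adverse events".

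**The concern.** Restricting a randomised comparison to patients who share an event after randomisation keeps the arms comparable only if allocation does not affect that event. Here allocation is meant to affect it. Patients between the two triggers are those whose management differs most between arms. Item 3 mostly keeps them in the liberal arm and mostly drops them from the restrictive arm. The restrictive patients who remain are therefore the more anaemic ones and, on the protocol's own account of anaemia, probably at higher risk.

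Section 16.8 uses these subsets to judge robustness. A subset that leans towards the trial's hypothesis could appear to confirm a chance positive result, suggest a benefit among the transfused when the trial is null, or hide a real harm of the liberal strategy.

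**Working it through.** **The plan's own figure.** The protocol gives no figure for item 3. The nearest anchor is the sample size in section 16.1 (14% versus 20%, two-sided 0.05, 85% power, 1.5% attrition, one interim analysis). A fixed design needs 703 per arm. With the boundaries in section 16.6 (2.75 and 1.98) it is 709 evaluable per arm; 709/0.985 = 719.8, so 720 per arm and 1,440 in total, as stated. I use 709 evaluable per arm below. Sections 4 and 5 carry larger totals (1,760 and 1,802). A larger trial would leave the risk ratios below unchanged and raise the chance of nominal significance.

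**Assumptions.** The protocol gives neither the proportion transfused in each arm nor the risk by lowest haemoglobin (Hb). All such values below are assumed. The strategy is taken to have no effect on any patient, so an unbiased analysis has an expected risk ratio (liberal over restrictive) of 1.00.

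**Model 1: sharp split at 75 and 95 g/L.** Let f1 and r1 be the share and risk with lowest Hb below 75, and f2 and r2 those for 75 to 95.

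Null RR = [(f1·r1 + f2·r2)/(f1 + f2)] / r1

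- Central case, f = 0.50 and 0.20, r = 0.25 and 0.14: (0.125 + 0.028)/0.70 = 0.219, and 0.219/0.25 = **0.87**.
- Strongest corner, f = 0.35 and 0.30, r = 0.30 and 0.12: (0.105 + 0.036)/0.65 = 0.217, and 0.217/0.30 = **0.72**.
- Mildest corner, f = 0.55 and 0.15, r = 0.22 and 0.16: (0.121 + 0.024)/0.70 = 0.207, and 0.207/0.22 = **0.94**.

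**Blurring the split, central risks.** If only two-thirds of the middle group are transfused under liberal: (0.125 + 0.0187)/0.633 = 0.227, giving 0.227/0.25 = **0.91**. If a fifth of that group are also transfused under restrictive: (0.125 + 0.0056)/0.54 = 0.242, giving 0.227/0.242 = **0.94**. Both assume that those transfused carry the middle group's average risk. Patients transfused during ischaemia, organ failure or bleeding may be at higher risk, in which case blurring would remove less of the bias.

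**Model 2: transfusion types.** Let a be the share transfused under either strategy, l the share transfused only under liberal, and g the risk of the first group relative to the second. The overall event risk is 17% in both arms, and never-transfused patients have the same risk as the second group.

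Null RR = (a·g + l) / [(a + l)·g]

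For a = 0.50, l = 0.20, g = 2: 1.2/1.4 = 0.86. Brackets give the chance of p<0.05 in favour of liberal; without bias it is about 2.5%.

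| Transfused, restrictive / liberal | g = 1 | g = 1.5 | g = 2 | g = 3 |
|---|---|---|---|---|
| 55% / 65% | 1.00 | 0.95 (6%) | 0.92 (9%) | 0.90 (14%) |
| 50% / 70% | 1.00 | 0.90 (11%) | 0.86 (21%) | 0.81 (39%) |
| 45% / 75% | 1.00 | 0.87 (17%) | 0.80 (37%) | 0.73 (68%) |
| 40% / 80% | 1.00 | 0.83 (24%) | 0.75 (55%) | 0.67 (88%) |

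With g = 0.8, meaning that patients transfused only under liberal are at higher risk, the ratio is 1.04 to 1.13 and the bias favours restrictive.

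**Model 3: continuous lowest Hb.** Normal, mean 76 to 84 g/L, SD 12, sharp split, logistic risk. An odds ratio of 1.35 per SD lower Hb gives 0.79 to 0.85; 1.65 gives 0.70 to 0.77; 2.23 gives 0.59 to 0.69. With no gradient the ratio is 1.00.

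**The case against.** A reader might infer that item 3 will show a spurious benefit of liberal transfusion. The documents do not support that. The bias needs a risk gradient, and section 7.1 reports an association without a size. Mild assumptions leave ratios of 0.90 to 0.95, which would usually not reach significance.

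A reader might also infer that the restrictive subset holds only patients who fell below 75 g/L, and that those between the triggers are lost from one arm only. That is too sharp:

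- Section 11.1 lets both triggers rise during listed derangements.
- Section 11.6 allows discretionary transfusion during rapid blood loss in either arm.
- Section 11.5.2 recognises transfusion without a trigger.
- Section 11.5.1 counts a repeat value above the threshold as adherent without transfusion.
- Patients between 85 and 95 g/L only on the ward reach neither standard trigger.

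These routes weaken the asymmetry but do not remove it.

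The consequence is also limited. The trial's conclusion rests on the intention-to-treat chi-squared test, and item 3 is one of six supportive subsets with no decision rule. Items 1, 4 and 6 also select on events after randomisation. Section 18.1.2 promises a published analysis plan before data lock, where a caution could be added. All of this stands and keeps the point modest. It does not rescue item 3: the protocol already fixes the exclusion, and item 3 selects on receipt of the very treatment that the allocated threshold governs.

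**Conclusion.** The point holds in this form. Item 3 compares groups that are not exchangeable, because allocation largely determines who enters them. The expected bias is probably towards liberal, given the protocol's own statement on anaemia. Its size cannot be derived from the protocol. The assumed shares and gradients mostly give a null risk ratio of about 0.72 to 0.95. Widely separated transfusion rates or steep gradients go lower, blurring moves the ratio towards 1, and with no gradient it is 1.00. Most of these calculations use an unblurred split and so probably lie towards the upper end of the bias. Against a design effect of 0.70, the artefact could still be a material part of the effect sought. Agreement between item 3 and the primary result would therefore not be evidence of robustness. The primary analysis is untouched.

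**What to change.** Delete item 3 from section 16.8 and rely on item 2 as the analysis of patients in whom the strategies could differ. Item 2 applies one criterion (Hb below 95 g/L) to both arms and depends far less on allocation, since Hb generally crosses 95 g/L before management diverges. If the criterion were fully independent of arm, the expected null risk ratio would be 1.00. State its limits beside it: Hb is measured after randomisation in an open-label trial, and a liberal patient could be transfused under a raised trigger before reaching 95 g/L.

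If item 3 is kept, label it descriptive and not evidence of robustness. An instrumental-variable estimate for any transfusion is not a sound replacement. Allocation also changes the timing and number of units in patients transfused under either strategy, so its effect does not run only through being transfused at all.

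The cost is one line in the protocol, with no new data or patients. The downside is the loss of one familiar table. The change is most credible if made before outcomes by arm are seen.

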#### 16.9 Missing Values

While we anticipate that the primary outcome will be available in >95% of patients, if the primary outcome is missing in more than 5% of patients, we will perform analyses to mitigate the effect of missing data as follows: we will develop a missing data model and perform a multiple imputation analysis. We will also carry out inverse-probability weighting. This is a two-stage model where a logistic regression model is first used to estimate the probability of not being missing. Then the analysis of the outcome proceeds on complete cases through a weighted analysis where the inverse probability of "completeness" forms the weights. The inference of the imputed model and inverseprobability weighting will be compared to that of the model with missing data.

#### 16.10 Health Economic Evaluation

The Health Economic analyses will be performed by researchers at the University of Leicester. We will adopt a partially pooled approach. Our base case analyses will be taken from the UK NHS and Personal Social Services (PSS) perspective. We will collect itemised resource usage data from all trial sites and cost them in the UK prices using published sources; British National Formulary (BNF), National Reference Costs, and the Personal Social Services Research Unit (PSSRU). For sensitivity analyses, we will cost resource usages from individual country health care provider perspectives and use Purchasing Power Parity (PPP) to exchange all prices into a common currency. Outcome data will be presented as incremental cost per quality-adjusted life years (QALYs) and per composite outcome avoided over 12 month time horizon. Quality of life will be measured by EQ5D-3L and will be collected at start of the trial, at discharge, and every 3 months thereafter.

The EQ5D-3L questionnaire will be translated into utility scores by using the UK tariff for (baseline analyses and using each individual country tariffs in sensitivity analyses). Resources usage will be collected during the trial including length of hospital and ICU stay, medication, units of blood cell transfusion through case report form and hospital electronic record systems. Post-discharge resources usage will be collected through postal questionnaire at 3 months after discharge including medication, primary care consultations, Accident and Emergency (A&E) visits, outpatient attendances, and hospital re-admissions. Hospital stay information will be extracted from electronic recorded data at the end of the trial. The rest will be collected using a tailed version of CSI at 6th months. The resource usage questionnaire will be redefined after the pilot stage. All itemised resource usage data will be costed using published national data (BNF, National reference cost, and PSSRU) at base case analyses. For sensitivity analyses, we will cost those based on individual participant countries' price and use purchasing power parity to translate those into a common currency.

Cost and QALYs will generated using area under the curve approaches. Generalised linear model will be used to compare differences in costs and QALYs. Bootstrapping methods will be employed to produce incremental cost effectiveness ratio and associated confidence intervals around the estimates. Missing value will be imputed using multiple imputation methods.

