Trial intervention	• Group 1: Restrictive transfusion strategy: patients will receive a RBC transfusion if their Hb concentration is <75 g/L (<7.5 g/dL; <4.7 mmol/L) intraoperatively and/or postoperatively.				
	• Group 2: Liberal transfusion strategy: patients will receive a RBC transfusion if their Hb concentration is <95 g/L (<9.5 g/dL; <5.9 mmol/L) intraoperatively, or postoperatively in the ICU; and/or <85 g/L (< 8.5 g/dL; <5.3 mmol/L) on the ward.				
Accrual period	24 months recruitment + 6 months follow up.				
Trial duration	01 February 2023 – 31 January 2026 (36 months).				
Assessments	Both investigational arms will be followed during their index hospitalisation or to postoperative day 28, whichever comes first; thereafter for 6 months postoperatively to assess clinical outcomes and mortality. Routinely collected healthcare data (Office for National Statistics, ONS) will be used to ascertain mortality at 6 months in UK participants.				

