#### 13.5 3 month Follow-up

- EQ-5D-3L
- Health Economics questionnaire

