- 14. **Healthcare resource use:** We will collect information on length of stay, time on ICU, units of red blood transfusion, procedures, laboratory tests, examination and medication during hospital stay using case report forms and electronic record systems. A resource usage questionnaire will be designed to collect resource usage information after discharge covering medication, primary care consultation, outpatients attendances, A&E visits and hospital readmission
- 15. **Quality of Life:** We will measure QoL using the EuroQol-5D-3L (EQ-5D-3L). The EQ-5D-3L includes five dimensions: mobility, self-care, usual activities, pain/ discomfort, and anxiety/ depression, each scored on three levels. We will apply the individual country's tariff and scoring algorithm to translate EQ-5D-3L scores to utility scores. This will be used to generate Quality Adjusted Life Year (QALY) profiles for the cost-effectiveness analysis.
- 16. **Clinical events:** The number and type of clinical events (more commonly referred to as 'adverse events' in the UK arm) will be recorded on the eCRF and reviewed by a Central Adjudication Committee (refer to section 17.6).

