# 24. Appendices

## 24.1 Schedule of events

Assessment	Screening	Pre- operative	Index Cardiac Surgery	Post-operative (ICU, Ward)	3 months	6 months	After LPLV (UK arm of the trial)
Trial Day/Month	-90 to 0	-30 to 0	Day 0	Postoperative period: day of surgery until hospital discharge or postoperative day 28	3 months +/- 21 days after Day 0	6 months +/- 21 days after Day 0	
Observation/							
Procedure							
Inclusion/exclusion	Х						
Informed consent	Х						
Pregnancy test 	X 						
Demographics		Х					
Medical/cardiac history		Х					
Height and weight		Х					
EuroSCORE I	Х	Х					
Randomisation		Х					
Surgical details			Х				
Intervention							
(transfusion strategy) applied 			XXXXXXXXXXXXXXXX 				
Trigger event & transfusion details collected 			XXXXXXXXXXXXXXXX 				
Preoperative laboratory values 		X 					
Intraoperative laboratory values 			X 				
Postoperative laboratory values 				X 			
ECG 		X 		X 		X 	
Concomitant							
medications		X				Х	
Clinical events			XXXXXXXXXXXXXXXXXXXXXXXXXXXXXXXXXXXXXX			X 	
EQ-5D-3L		Х		X	Х	X	
Health economics		^		1 "		^	
questionnaire					Х		
Routine data linkage							Х

Page **53** of **55** 

IRAS ID: 325425

Women of childbearing potential.

All protocol defined "trigger events" and all red cell transfusions will be recorded in the eCRF from the start of the index surgical procedure until hospital discharge, as well as the pre- and post-event/transfusion Hb, times, and values. All nonred cell transfusions administered during the index hospitalisation period will be reported in the eCRF.

Hb, haematocrit, platelets, INR, aPTT, fibrinogen, creatinine, and CK-MB or troponin (preferred).

Lowest Hb (pre/during CPB and chest closure), lowest HCT (pre/during CPB and chest closure), lowest arterial and mixed venous pO2 (pre/during CPB and chest closure), lowest arterial and mixed venous O2 saturation (pre/during CPB and chest closure), lowest cardiac index (pre-CPB and chest closure) if measured, minimum pump flow (during-CPB).

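### Section 16.10 promises 12-month cost-effectiveness results from data that end at 6 months, and names a 6-month resource-use instrument that the visit list and schedule omit

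*Protocol*

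**What the plan says.** **Horizon.** Section 16.10 (Health Economic Evaluation) says results will be given as incremental cost per QALY and "per composite outcome avoided over 12 month time horizon". It adds that EQ-5D-3L data "will be collected at start of the trial, at discharge, and every 3 months thereafter", without saying when that series ends. Costs and QALYs are to come from an area-under-the-curve calculation, with multiple imputation for missing values.

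**Follow-up.** The protocol summary (Section 4) gives the accrual period as "24 months recruitment + 6 months follow up" and says participants are followed through the index stay and "thereafter for 6 months postoperatively to assess clinical outcomes and mortality". In the schedule of events (Section 24.1) the last participant contact is "6 months +/- 21 days after Day 0". The only later column is UK routine data linkage after the last participant's last visit. Section 15.1 defines the composite within 6 months of surgery.

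**Resource use.** Section 16.10 describes a postal questionnaire at 3 months after discharge and an electronic extraction of hospital stays at the end of the trial, and then says: "The rest will be collected using a tailed version of CSI at 6th months". The visit lists place the "Health Economics questionnaire" under the 3-month follow-up (Section 13.5) and not under the 6-month follow-up (Section 13.6). The schedule of events also marks it at 3 months only. Section 19.4 describes only the 3-month postal form.

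**Tariff.** Section 16.10 assigns the UK tariff to the main analysis and country tariffs to sensitivity analyses. Section 19.5 says the individual country's "tariff and scoring algorithm to translate EQ-5D-3L scores to utility scores" will be applied, and does not mention the UK tariff.

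**The concern.** An area-under-the-curve QALY needs utility measurements up to the end of its horizon. If the horizon is 12 months and the last measurement is at 6, the second half of every participant's curve has no data behind it. The cost per composite outcome avoided has the same problem, because the composite is defined and collected only to 6 months.

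The resource-use gap is separate. Sites work from the visit list and the schedule. If a form is named only in the economic methods section, it is likely not to be sent, and community care not recorded at the time cannot be reliably rebuilt later. The base case takes an NHS and Personal Social Services perspective, in which primary-care and outpatient contacts are cost items.

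The economic evaluation is embedded in the UK arm, and the scientific abstract lists costs, quality of life and cost-effectiveness among the secondary outcomes. The stated result should therefore be one that the collection plan can deliver.

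**Working it through.** No power or sample-size formula applies. The check sets the stated horizon against what is scheduled, then against the calendar.

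**1. What is collected, and until when**

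| Input | Last planned collection | Where stated |
|---|---|---|
| Horizon of the economic results | 12 months | Section 16.10 |
| EQ-5D-3L | 6 months (before surgery, after surgery, 3 and 6 months) | Sections 13.2, 13.4 to 13.6; schedule |
| Composite endpoint | 6 months | Sections 14.12.2, 15.1 |
| Emergency visits, admissions, current medications | 6 months | Sections 13.6, 14.12.2 |
| Health economics questionnaire | 3 months | Sections 13.5, 19.4; schedule |
| Further resource-use instrument | 6 months | Section 16.10 only |
| Hospital stays, electronic extraction | end of trial | Section 16.10 |
| UK mortality by linkage | request made after last participant's last visit, for 6-month mortality | Section 19.4 |

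**2. Coverage of the horizon by utilities**

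Coverage = last measurement / horizon = 6 / 12 = 50%.

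At the late edge of the visit window, 21 days is 21 / 30.4375 = 0.69 months, so coverage is 6.69 / 12 = 56%.

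At full health throughout, the observed area is at most 6 / 12 = 0.5 QALY, against 1.0 QALY over 12 months.

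**3. Calendar**

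The scientific abstract (Section 5) has recruitment in months 8 to 30, follow-up to month 35 and closedown by month 36.

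- A participant recruited in month 30 reaches 12 months at 30 + 12 = month 42, which is 6 months after the project ends. That participant has 35 − 30 = 5 to 36 − 30 = 6 months available.
- If recruitment is uniform over months 8 to 30 (an assumption), the share reaching 12 months is (35 − 12 − 8) / (30 − 8) = 15 / 22 = 68% by month 35, and (36 − 12 − 8) / 22 = 16 / 22 = 73% by month 36. No EQ-5D-3L, questionnaire or event collection is scheduled for them at that point.

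**4. Resource use within the observed 6 months**

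If sites follow the visit list and schedule alone, the questionnaire reaches about 3 / 6 = 50% of the observed period. For months 3 to 6, Section 13.6 still brings in emergency visits, admissions and a medication list. Of the items in the 3-month questionnaire, that leaves primary-care consultations and outpatient attendances uncollected, together with medication changes between the two contacts.

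**The case against.** **The interval has no stated end.** Three-monthly EQ-5D-3L collection in Sections 16.10 and 19.4 could be read as continuing to 12 months. The visit lists and the schedule contain no 9- or 12-month contact, and the project calendar could not hold one for late recruits. The phrase may show what was intended, but it does not provide the data.

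**A separate plan will follow.** Section 16.5 defers the health economic outcomes to their own analysis plan, and an extrapolation model could properly sit there. Its absence from the protocol is therefore no fault. However, visit content and length of follow-up are set in the protocol, and an analysis plan cannot recover observations that were never scheduled. Multiple imputation does not help either, because utilities for months 6 to 12 are missing by design in everyone.

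**The questionnaire is provisional.** Section 10.2 says the pilot will refine the resource-use questionnaire and how often it is used, and Section 16.10 says it will be revised after the pilot. This stands, and it makes the 6-month omission easier to repair. Until then, the current text asks for a 6-month instrument in one place and leaves it out in three.

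**Some data may run later.** End-of-trial hospital extraction and UK linkage could extend past 6 months for early recruits. That also stands, but neither source yields utilities or community care.

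**Stronger readings to avoid.** A reader might infer that all cost data for months 3 to 6 are lost. Sections 13.6 and 14.12.2 show otherwise for medications, emergency visits and admissions. A reader might also infer two competing base cases from the tariff sentences. Section 19.5 does not mention a base case, and Section 16.10 already sets the order, so this is a wording conflict only.

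**Conclusion.** The 12-month horizon in Section 16.10 contradicts the rest of the protocol. Half of it (6 of 12 months, or 44% at the late edge of the visit window) has no utility data in any participant. The 12-month within-trial cost per QALY and cost per composite outcome avoided cannot be produced from the planned collection.

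It would go too far to conclude that no cost per QALY can be produced. EQ-5D-3L at baseline, after surgery, 3 and 6 months, together with the 6-month composite, supports a 6-month result.

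The second defect is a mismatch over the 6-month resource-use instrument. It puts primary-care and outpatient use in months 3 to 6 at risk, on the assumption that sites follow the visit list and schedule as written. The tariff wording is a minor matter of alignment.

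The clinical primary endpoint, the sample size and the primary analysis are not touched.

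**What to change.** 1. In Section 16.10, state the within-trial horizon as 6 months from surgery for both cost per QALY and cost per composite outcome avoided. Label any 12-month result as a model-based extrapolation.
2. Add the 6-month resource-use form to Section 13.6, to Section 19.4 and to the 6-month column of the schedule of events, so that they agree with Section 16.10.
3. As a minor alignment, make the tariff sentence in Section 19.5 match Section 16.10: UK tariff in the base case, country tariffs in sensitivity analyses.

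The cost is a shorter observed horizon, one extra form at a contact that already takes place, and a wording amendment. Keeping 12 months as an observed horizon would instead need contacts after month 6, which for the latest recruits fall up to 6 months after the project closes.
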